### 8.1.1 Quantitative outcomes of interventions

The primary (i.e., caries arrest, tooth pain / sensitivity) and secondary outcomes (i.e., presence of new decay, oral health-related quality of life) measure the effectiveness of the study interventions. The process outcome are to access the safety of the interventions and to ascertain patient satisfaction with the treatment 1 year after the initial treatment.

**Primary outcome: Older adults caries arrest and tooth pain / sensitivity (Arm 1: SDF vs. Arm 2: ART + FV) will be assessed through:**

- Clinical dental exam: will be performed at the two intervention time points (T0, T26) and final time point (T52) by a trained and calibrated dental hygienist according to the International Caries Detection and Assessment System II (ICDAS-II). The exam will be used to identify a change in oral health status between the Baseline visit and the 26-week visit (T0 and T26) as well as the 26-week visit and the 52-week visit (T26 and T52).
- Self-reported evaluation: Scales on tooth pain / sensitivity (PROMIS v.1.0, Health Organization; Dental Discomfort Questionnaire (DDQ)) will be used to measure levels of change in oral pain / sensitivity improvement. Higher scores on the PROMIS and DDQ

indicate increased tooth pain / sensitivity. These measures will be conducted during the baseline visit, 26-week visit, and 52-week visit ( $T_0$ ,  $T_{26}$ , and  $T_{52}$ ).

**Secondary outcomes: Older adults' new decay and GOHRQoL (Arm 1: SDF vs. Arm 2: ART +FV) will be assessed through:**

- Clinical dental exam: A newly carious tooth is defined as any tooth receiving an ICDAS lesion code  $\geq 3$  that received a sound code on the previous dental exam or any tooth surface with an ICDAS filling code  $\geq 3$  that previously did not have one. The number of teeth with new decay or filling will be assessed through clinical dental exams ( $T_0$ ,  $T_{26}$ , and  $T_{52}$ ) and recorded on the ICDAS Assessment form.
- Self-reported evaluation: The Geriatric Oral Health-related Quality of Life (GOHRQoL) consist of 12 questions and will be used to assess the impact of the intervention on participants overall oral health quality of life. The overall score will be calculated with higher scores indicating that the participant has greater oral health Quality of Life. The measures will be collected within two week of the baseline visit, the 26-week visit ( $T_0$ ,  $T_{26}$ ), and 52-week visit exam ( $T_{52}$ ).

**Process outcome: Safety and satisfaction and moderating variables (Arm 1: SDF vs. Arm 2: ART +FV) will be assessed through:**

- The Safety Questionnaire-Revised for Adults consists of 15 main adverse events (i.e., existence of dental insurance, severity of adverse symptoms after receiving the dental treatment) and will be used to identify adverse events. Participants will complete this survey pre- and post-exam/treatment at the baseline visit, 26-week visit, and the 52-week visit, respectively. The treatment satisfaction will be assessed through the treatment satisfaction questionnaire for medication (TSQM) modified for Dental and satisfaction with new treatment for cavities, comprised of six questions. The overall average score will be assessed from these two scales with higher mean score indicating better satisfaction with the study treatment. The measures will be conducted during the baseline visit, follow-up visit, and final exam ( $T_0$ ,  $T_{26}$ , and  $T_{52}$ ).

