##### **Arm 2 (N=275 participants): A “typical dental strategy” consisting of ART + FV**

Atraumatic Restorative Treatment (ART) will be a modification of the approach used by Lo and colleagues (2006), and the cavity restored at baseline with resin reinforced glass-ionomer cement (GIC) (GC Corporation, Japan).

Participants in this arm will also receive biannual topical fluoride varnish application (FluoriMax, Elevate) according to manufacturer's instructions.

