### 5.1 Subject *Initial* Inclusion Criteria

In the first stage of the enrollment process, an individual must meet all of the following criteria:

- Provide signed and dated informed consent form
- Willing to comply with all study procedures and be available for the duration of the study (1 year)
- Male or female, aged 62 years or older
- Live in a participating older adult housing facility

In the second stage of enrollment process, additional inclusion criteria for continuation and participation in the RCT is based on the dental screening:

- Have at least one untreated root or coronal caries lesion on any permanent tooth with an International Caries Detection and Assessment System (ICDAS) II active lesion score of 3 or greater (localized enamel cavity to extensive cavity).

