### 5.4.2 Masking Procedures (IR-6)

We will attempt blinding of participants to the study group, but this may not be possible due to SDF color change.

The hygienists will be unaware of the treatment assignment when they go to their respective housing facilities. For all treatment visits, assessments will be conducted prior to the intervention delivery.

Two hygienists will go to the housing facility randomized to the SDF arm and the other two will go to the ART + FV arm. The baseline treatment to be applied will be revealed only after the baseline caries exam has been completed. At the 6 month follow-up visit, the two hygienists that applied SDF will now go to the facilities randomized to the ART + FV facilities and vice-versa to conduct the 6-month follow up caries assessment exam and treatment. We will follow similarly for the 12-month follow-up visit. By this strategy, we will make sure that potential bias of the hygienist evaluating their own work is minimized. Additionally, periodically we will check for the quality of the assessment data by [name] randomly examining 20% of the participants.

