### **6.7 Administration of Intervention**

Arm 1: Topical application of 38% silver diamine solution to ICDAS lesions code 3-6.  
Arm 2: Atraumatic Restoration Treatment (ART) to ICDAS lesions code 3-6, followed by topical fluoride varnish (FV) to all teeth.

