### **Baseline Dental Exam**

- Dentists will administer the Safety Questionnaire (Pre-Exam).
- Hygienists will perform initial dental exam examination at participant's respective housing facility to determine eligibility to continue in the clinical trial based on caries status.
- Study staff will record results of dental exam examination.
- Hygienists, under the direction of the study dentist, will proceed as follows:
- If the participant has an urgent cavity or another serious dental problem, they will be instructed to go for dental care immediately and their participation will end.
- If the participant has no cavities or other urgent problems, they will be instructed to continue regular visits with their dentist and their participation will end.
- If the participant has cavities that require treatment but no urgent problems, they will receive one of two treatments at this visit and will continue to participate in the research. Hygienists will administer the intervention treatment (based on study arm) to all untreated active root or coronal carious lesion with ICDAS-II lesion severity code of 3 or greater.
- If a participant reports any issue with the applied treatment within one week of the treatment date, the study team will return to the housing facility to examine and correct the treated tooth as needed. Within 48 hours, the study team will call the participant to ask the participant if the issue has been resolved and will administer a paper safety questionnaire. The completed paper safety questionnaire will be stored in the CRF folder and documentation of the return visit/treatment will be added to the participant's electronic record.

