Secondarily, we will extend the above GEE approach to analyze the repeated (baseline, 26 and 52-week) measures for each outcome. The models for each outcome will include the same prognostic variables as before, as well as time and a time by treatment interaction. We will allow for correlations among the repeated measures, e.g., using a first-order autocorrelation structure. If a substantial within-facility correlation is found we may need to incorporate facility as a second cluster levels (within which person – the first cluster level – is nested). We will estimate and test (via a robust t-test) the interaction term to compare trends over time for the two interventions. If the use of two cluster levels is not found to be feasible in the GEE approach, we will consider a generalized mixed effects model approach.

**Causal Inference standards (CI-1, CI-2, CI-3, CI-4):** Our use of randomization and adjustment in regression models should be sufficient to provide causally interpretable intervention effect estimates; special causal inference techniques such as propensity score or instrumental variable methods often indicated for observational studies, will therefore not be necessary for our data analysis. We will avoid biases in causal inferences about the intended interventions by using an intent-to-treat approach, in which individuals are analyzed according to randomized groups without regard to (extent of) treatment actually received.

**Sensitivity Analyses IR-5:** We will check sensitivity of conclusions to model assumptions as well as methodological decisions such as outcome definition. In particular, for the arrest outcome, our primary analysis is based on a binary indicator of 'complete' arrest of all lesions for an individual. We will seek to corroborate results from this approach with an alternative approach analyzing

number of lesions arrested. For the GEE analyses, planned for all outcomes, sensitivity will be assessed in part by using alternative working covariance structures and alternative sets of predictors. For some outcomes, alternative distributions will be considered; for example, for number of arrested lesions, possible distributions include Poisson, negative binomial, zero-inflated Poisson (ZIP), and zero-inflated negative binomial (ZINB). Sensitivity to assumptions regarding missing data will also be investigated as described further below.

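### The new-decay definition does not exclude fillings placed by the study, so Arm 2 restorations can score as new decay at week 26 if glass ionomer is coded 3 or more

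*Combined protocol and SAP*

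**What the plan says.** **Definition (8.1.1, secondary outcomes).** A tooth is newly carious by either of two routes: a lesion code of 3 or more on a tooth "that received a sound code on the previous dental exam or any tooth surface with an ICDAS filling code" of 3 or more that was not there before. The next sentence confirms that fillings enter the count: "The number of teeth with new decay or filling will be assessed through clinical dental exams".

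**Who is treated, and with what.** The entry criterion in 5.1 is "Have at least one untreated root or coronal caries lesion on any permanent tooth", with an active ICDAS score of at least 3. At baseline the hygienists "will administer the intervention treatment (based on study arm) to all untreated active root or coronal carious lesion" of that severity (7.1). In Arm 2, section 4.2 has "the cavity restored at baseline with resin reinforced glass-ionomer cement". Arm 1 receives "Topical application of 38% silver diamine solution to ICDAS lesions code 3-6" (6.7), which leaves no filling.

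**Order of events.** Section 5.4.2 states: "The baseline treatment to be applied will be revealed only after the baseline caries exam has been completed".

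**Use of the outcome.** Sections 4 and 11.1 make new decay at 12 months part of the secondary hypothesis that SDF is non-inferior. Table 8.1.1 lists it at baseline, 26 and 52 weeks. Section 11.4 also plans a GEE model to "analyze the repeated (baseline, 26 and 52-week) measures for each outcome". It treats secondary outcomes as exploratory and gives no numeric margin for them.

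**The concern.** The two routes are not built alike. The lesion route asks for a sound code at the preceding exam, so disease already present at entry cannot count. The filling route asks only that the filling is new. It requires neither a previously sound surface nor a filling placed outside the study.

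Restoring an existing lesion is the assigned treatment in Arm 2 and no part of the treatment in Arm 1. Read literally, the definition can therefore score treatment as disease in one arm only. A higher Arm 2 count makes SDF look better, which is the direction that supports non-inferiority.

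**Working it through.** The documents give no SD, expected count, power or margin for new decay, so there is no figure of the plan to reproduce. The check applies the written rule to the visit sequence.

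**Step 1. Follow one surface** that has a lesion coded 3 or more and no filling at baseline.

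| | Arm 2 (ART + FV) | Arm 1 (SDF) |
|---|---|---|
| Baseline exam | lesion, no filling | lesion, no filling |
| After the exam | glass ionomer placed | SDF applied |
| Week-26 exam | filling present | no study filling |
| Lesion route | not met: not sound at baseline | not met: not sound at baseline |
| Filling route | met, if glass ionomer is coded 3 or more | not met |

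A surface that already carried a qualifying filling code at baseline does not meet the filling route in either arm.

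**Step 2. Which counts are touched by baseline restorations?**

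- Baseline to week 26: yes.
- Cumulative, baseline to week 52: yes.
- Repeated-measures model in 11.4: yes, because it uses the week-26 measure.
- Week 26 to week 52, each exam against the one before: no, because the filling was already recorded at week 26.

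The last line depends on what is placed at week 26. Section 6.11 lists ART at baseline and only varnish at both visits. Section 7.2 has arm-based treatment of previously treated and newly found lesions at week 26. Any restoration placed then could reach the second interval. A lesion first counted at week 26 could also score again as a filling at week 52.

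**Step 3. Is an exclusion stated elsewhere?** None was found. Section 13.2.2 mentions longitudinal coding of the exam data, 15.2.2 mentions checking derived variables against specifications, and Figure 15.3.1 lists a treatment log. None says how study restorations are handled. Section 13.2.1 withholds baseline results from the follow-up examiners, so they cannot use those results to tell study restorations from others.

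**Step 4. Direction and size (illustration only).** Take one treated tooth per participant, the minimum at entry, a count that spans baseline to week 26, and glass ionomer coded 3 or more. Let

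- u = share of treated teeth with a restored surface that was previously unfilled (assumed, 0 to 1);
- r = share of study restorations still present at week 26;
- o = share of treated teeth filled outside the study when no study filling is present, taken as equal in both arms and independent of restoration loss.

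False counts per participant:

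- Arm 2: u × [r + (1 − r) × o]
- Arm 1: u × o
- Difference: u × r × (1 − o)

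For r, take 0.87 to 1. The 0.87 is the ART survival rate in 2.1, borrowed from a root-caries trial whose reference title gives 12 months. For o, take 0 to 0.40. The 0.40 is 1 − 0.60, where 60% is the share in 4.1 with no or rare dental visits; it describes visit habits and is not a filling rate.

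| u | r = 0.87, o = 0.40 | r = 1, o = 0 |
|---|---|---|
| 0 | 0 | 0 |
| 0.5 | 0.5 × 0.87 × 0.60 = 0.26 | 0.50 |
| 1 | 1 × 0.87 × 0.60 = 0.52 | 1.00 |

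The difference cannot be negative under equal outside-filling shares. With unequal shares it reverses only if the Arm 1 share exceeds r + (1 − r) × (the Arm 2 share), which is never less than r.

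**The case against.** **The deciding premise is not in the documents.** No table of filling codes is given. The threshold of 3 shows that some filling codes were meant to be left out, and glass ionomer could be among them. This stands, and it makes the finding conditional.

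**The exclusion may be written elsewhere.** The training protocol cited in 13.2.1, the Data Validation Plan in 13.2.2 and the derivation specifications in 15.2.2 are not available to this review. This stands too. A reader might infer that the trial has no exclusion at all; the documents support only that 8.1.1 and the rest of the available text state none.

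**Exam-to-exam comparison is the natural reading.** The lesion route names the previous exam, and 8.1.1 describes change from baseline to week 26 and from week 26 to week 52. On that reading baseline restorations add nothing to the second interval. This limits where the problem acts but does not remove it: the count that tests the 12-month hypothesis is not specified, and the first interval enters the repeated-measures model.

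**Many treated surfaces may already be filled.** Section 2.1 says that most decay in older adults is failure of restorations at the gum line and in exposed roots. Such surfaces could be exempt, so it would be wrong to infer that every restored Arm 2 tooth is miscounted.

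**Outside fillings occur in both arms.** The written rule also counts an outside filling of a lesion already on record, which narrows the gap between arms. The week-26 referral sheets come after the week-26 exam, so they cannot explain fillings seen at that exam.

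**The outcome is secondary and exploratory.** This is true and limits the consequence. It does not make it acceptable for a stated rule to score one arm's treatment as disease.

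**Conclusion.** The concern holds, conditionally. As written, the filling route counts an Arm 2 baseline restoration on a previously unfilled surface as new decay at week 26, provided glass ionomer has a filling code of 3 or more. Study treatment adds no such counts in Arm 1. The effect inflates the Arm 2 count in the baseline-to-week-26 interval, in any cumulative count to week 52 and in the repeated-measures model. It favours SDF on the secondary non-inferiority hypothesis.

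The size cannot be determined from the documents and may be zero. The values in step 4 rest on assumed u and o, a borrowed r and one treated tooth per person; they show direction and are not estimates. A reader might infer that the 12-month comparison is certainly biased, or that the trial's main conclusions are at risk. The documents support neither: the 12-month count is unspecified, and caries arrest and tooth pain do not use this definition.

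This should be fixed, because the rule is stated, its expected direction is known and the repair is cheap. Confidence is medium, given the missing code table and specifications.

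**What to change.** Amend 8.1.1 as follows, identically in both arms.

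1. A restoration placed by the study does not count as new decay, nor does a filling on a surface whose lesion was coded 3 or more at an earlier exam. Fillings on surfaces previously sound or coded below 3 continue to count, so that a small lesion that progresses and is filled outside the study is not lost. A lesion first counted at week 26 is counted once.
2. State the reference exam for a new filling (baseline or the preceding exam) and the count that tests the 12-month hypothesis.
3. Apply the rule at data derivation, from the exam charts and treatment log, so that examiners remain unaware of baseline results.

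If the training protocol or derivation specifications already contain the exclusion, cite it in 8.1.1. Sections 6.11 and 7.2 must be reconciled on treatment at week 26, because restorations placed then would also reach counts from week 26 to week 52.

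The cost is a few sentences and one derivation rule, with no new data. The documents do not say whether the treatment log records tooth and surface; if it does not, the baseline and 26-week charts identify the lesions already on record. The downside is that new decay at the margins of treated surfaces is left to the arrest outcome, and the protocol should say so.

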### Study Arm 2:

Application procedure for the atraumatic restorative treatment is as follows::

1. When the lesion is on the occlusal surface, the occlusion will be checked with blue articulating paper prior to other clinical procedures.
2. The field will be isolated with cotton rolls. Soft debris will be removed with moistened cotton pellets. Then soft demineralized tooth structure will be removed with a spoon excavator at the periphery of the lesion, where there is access. A *manual* brush and pumice will be used to remove any further loose material. The cavity will be washed well with water.
3. The cavity will be conditioned with the liquid of the glass ionomer (polyacrylic acid) for 10-15 seconds and then rinsed, maintaining moisture control throughout.

---

4. The resin reinforced glass ionomer restorative (Fuji II LC Automix, GC America) will be inserted into the cavity using the manufacturer's delivery device and then coated with Fuji Coat (GC America). The restoration will then be light cured for 20 seconds.

Following the restorative treatment, the patient will be treated with fluoride varnish, as below.

FluoriMax Varnish. By quadrant or arch, all of the teeth will be coated with fluoride varnish (FluoriMax, Elevate Oral Care) using the manufacturer's brush system. The varnish container will be shaken for a few seconds before application. A single application from posterior to anterior will be used and then the occlusal surfaces will be coated, with no reapplication. The material will be allowed to dry 3-5 seconds and the patient instructed to avoid eating or dental hygiene for 4 hours.

If a participant reports any issue with the applied treatment within one week of the treatment date, the study team will return to the housing facility to examine and correct the treated tooth as needed. Within 48 hours, the study team will call the participant to ask the participant if the issue has been resolved and will administer a paper safety questionnaire. The completed paper safety questionnaire will be stored in the CRF folder and documentation of the return visit/treatment will be added to the participant's electronic record.

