## **7.2 26-Week Visit (T26) (Day 168 to Day 196)**

### **Dental Exam and Treatment**

- Dentists will administer the Safety Questionnaire (Pre-Exam).

- Hygienists will perform dental examination at participant's respective housing facility to evaluate caries arrest and identify new decay.
- Study staff will record results of dental examination.
- Hygienists, under the direction of the study dentist, will administer the intervention treatment (based on study arm) for all previously treated lesions and newly identified active root or coronal carious lesion with ICDAS-II lesion severity code of 3 or greater.
- Study staff will give participants referral sheets with exam results and direction to follow up with their personal dentist for routine dental care.
- If a participant reports any issue with the applied treatment within one week of the treatment date, the study team will return to the housing facility to examine and correct the treated tooth as needed. Within 48 hours, the study team will call the participant to ask the participant if the issue has been resolved and will administer a paper safety questionnaire. The completed paper safety questionnaire will be stored in the CRF folder and documentation of the return visit/treatment will be added to the participant's electronic record.

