**Table 8.1.1 Quantitative Summary of measures, sources, and timeline (IR-4)**

Variable Type	Measure	Scale	Source	Timeline
Intervention by Study Arms	

• Biannual SDF (Arm 1)

• ART + biannual FV(Arm 2)

			$T_0, T_{26}$
Primary Outcome	Clinical dental exam 

• % freq of arrested surface/teeth

• Caries arrest

• overall score

		

• ICDAS Coronal and Root [Dikmen 2015]

	$T_0, T_{26}, T_{52}$

	Self-reported evaluation 
 
• Tooth pain/sensitivity
 
	
 
• overall score
 
	
 
• PROMIS v.1.0 - Pain Intensity 3a [Modified for Dental]
 
• Dental Discomfort Questionnaire [Modified for Adults from Versloot et al. 2006]
 
	T 0 , T 26 , T 52
Secondary Outcomes	Clinical dental exam 
 
• New decay
 
 Self-reported evaluation 
 
• OH-quality of life
 
	
 
• # freq of new decay teeth
 
• GOHRQoL overall score
 
	
 
• ICDAS Coronal and Root [Dikmen 2015]
 
• Geriatric Oral Health Quality of Life (GOHRQoL) [Atchison and Dolan, 1990]
 
	T 0 , T 26 , T 52 T 0 , T 26 , T 52
Process Outcome	
 
• Safety
 
• Satisfaction
 
	
 
• % freq. adverse event
 
• overall score
 
• overall score
 
	
 
• Safety Questionnaire (Pre- and Post-Exam/Treatment [Adapted for Adults from Milgrom et al. 2018]
 
• Treatment Satisfaction Questionnaire for Medication (TSQM) [Modified for Dental]
 
• Satisfaction with New Treatment for cavities [Modified for Adults from Crystal et al. 2017]
 
	T 0 , T 26 , T 52 T 52 T 52

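### Read literally, the lesion limb of the new-decay definition omits early lesions that progress to code 3 or above, and this can favour SDF if varnish slows such lesions

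*Combined protocol and SAP*

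**What the plan says.** Section 8.1.1 (secondary outcomes) defines a newly carious tooth by two limbs joined by *or*.

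- **Lesion limb:** a tooth with lesion code 3 or more "that received a sound code on the previous dental exam".
- **Filling limb:** "or any tooth surface with an ICDAS filling code" of 3 or more that was not there before. This limb has no sound-before condition and does not exclude fillings placed by the study.

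Table 8.1.1 gives the scale as "freq of new decay teeth", so the outcome counts teeth, although the filling limb is worded for surfaces.

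The documents do not define a sound code and never name codes 1 or 2. The only severity range they describe starts at 3: "active lesion score of 3 or greater (localized enamel cavity to extensive cavity" (Section 5.1).

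Section 7.2 has its own idea of a new lesion at 26 weeks, a "newly identified active root or coronal carious lesion with ICDAS-II lesion severity code of 3 or greater". It does not require the tooth to have been sound before.

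Coverage differs by arm (Section 6.7). Arm 1 is "Topical application of 38% silver diamine solution to ICDAS lesions code 3-6". Arm 2 is ART to the same codes, "followed by topical fluoride varnish (FV) to all teeth". Section 6.10 repeats that "all of the teeth will be coated with fluoride varnish".

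Sections 4 and 11.1 state a non-inferiority hypothesis for new decay. Section 11.4 plans confidence intervals for differences in means for outcomes other than the primaries, calls the secondary assessment exploratory, and gives no numerical margin.

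**The concern.** On a graded scale with a threshold at 3, a tooth can be neither sound nor at the threshold. The lesion limb has no rule for such a tooth. If it cavitates and is not filled, the event is lost.

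The rule is the same in both arms, but the teeth it drops are not treated alike: Arm 2 varnishes them and Arm 1 plans nothing for them. If varnish slows early lesions, the lost events fall more often in Arm 1, and the difference in mean new-decay teeth is pulled toward zero. In a non-inferiority comparison that is the anti-conservative direction. New decay is the only secondary clinical outcome, so its definition should not be left for the analyst to settle after seeing the data.

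**Working it through.** **No plan figure to reproduce.** Section 11.2 sizes the trial on tooth pain and arrest only. It gives no incidence, effect size, margin or power for new decay.

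**Step 1: which histories the lesion limb counts** (unfilled teeth, sound read as code 0, each exam compared with the one before).

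| Baseline | 26 weeks | 52 weeks | Counted? |
|---|---|---|---|
| sound | 3 or more | any | yes, at 26 weeks |
| sound | sound | 3 or more | yes, at 52 weeks |
| 1-2 | 3 or more | any | no |
| 1-2 | 1-2 | 3 or more | no |
| sound | 1-2 | 3 or more | no, at either exam |

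In the last row a tooth is sound at entry and cavitated at the end, yet never counts. In the third row a lesion that Section 7.2 could call newly identified at 26 weeks is not new decay in the outcome. If sound instead means below code 3, all five rows are counted.

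**Step 2: what is lost from the difference.** Let E be code 1-2 teeth per person, p their progression risk in Arm 1, and RR the Arm 2 to Arm 1 risk ratio in those teeth.

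Hidden difference (Arm 1 minus Arm 2) = E × p × (1 − RR)

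Every input below is an assumption; the documents supply none of them.

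- Counted part: 12 sound teeth, 5% incidence in Arm 1, RR 0.8 in sound teeth. Arm 1: 12 × 0.05 = 0.60. Arm 2: 0.60 × 0.8 = 0.48. Difference 0.12, rate ratio 0.60/0.48 = 1.25.
- Omitted part: E from 1 to 4, p from 10% to 20%. Low end E × p = 1 × 0.10 = 0.10; high end 4 × 0.20 = 0.80.

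| RR in code 1-2 teeth | Hidden difference, low to high | Full difference | Full rate ratio |
|---|---|---|---|
| 0.6 | 0.04 to 0.32 | 0.16 to 0.44 | 1.30 to 1.46 |
| 0.8 | 0.02 to 0.16 | 0.14 to 0.28 | 1.25 to 1.25 |
| 1.0 | 0 | 0.12 | 1.21 to 1.09 |
| 1.2 | −0.02 to −0.16 | 0.10 to −0.04 | 1.17 to 0.97 |

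Example, RR 0.6 at the high end: hidden 4 × 0.20 × 0.4 = 0.32; full 0.12 + 0.32 = 0.44; ratio (0.60 + 0.80)/(0.48 + 0.48) = 1.46.

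On the difference scale the omission favours SDF when RR is below 1, does nothing at 1, and works against SDF above 1. On the ratio scale it changes nothing when RR equals that in sound teeth.

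**Step 3: the filling limb.** Every randomised participant has at least one lesion of code 3 or more, and Arm 2 restores such lesions at baseline. If a study restoration carries a filling code of 3 or more (the documents do not say), it meets the filling limb at 26 weeks in Arm 2 only. One such tooth per person moves Arm 1 minus Arm 2 by −1, more than any hidden difference in Step 2.

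**The case against.** A reader might infer that new decay counts only teeth that were sound. It does not: the filling limb has no such condition, so a code 1-2 surface that progressed and was filled can still enter. What remains lost is unfilled progression.

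A reader might also infer that the rule biases the trial toward SDF and hides the preventive effect of varnish. The documents do not support that either. Varnish also covers the sound teeth, which are counted, so its effect is still measured. Section 2.1 credits both varnish and SDF with preventing new lesions and gives no effect size. As Step 2 shows, the sign depends on an unknown risk ratio. Nothing shows that the arms differ most in code 1-2 teeth.

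The best defence is that sound may simply mean below code 3, in which case nothing is lost. That is possible, but the text does not say it, and saying it would be most of the remedy.

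Finally, Section 11.4 already promises sensitivity checks on outcome definition. The example it develops is arrest; new decay is not named. That the outcome is exploratory and has no margin stands in full: there is no decision threshold for the omission to push a result across.

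**Conclusion.** The point holds in a limited form. With sound read as code 0, the lesion limb omits unfilled progression from code 1-2 to 3 or more and does not match the 26-week wording in Section 7.2. Because only Arm 2 has a planned agent on those teeth, the omission can shrink the difference in mean new-decay teeth toward SDF non-inferiority, on the condition that varnish slows early-lesion progression relative to Arm 1.

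Size and sign are not established. The figures in Step 2 show how the result depends on the assumptions; they are not estimates for this trial. The filling limb could matter more, but that rests on the unstated code given to study restorations. The primary outcomes are not touched. It is worth correcting because the remedy is cheap and the outcome carries a stated hypothesis.

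**What to change.** Before database lock, and without reference to results by arm:

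1. Define new decay as lesion code below 3 at the previous exam (or at baseline; state which) and 3 or more now, at one stated level, tooth or surface. Keep sound-to-3-or-more as a sensitivity analysis, with sound defined.
2. Confirm that the exam form records codes 1 and 2 separately. If it folds them into sound, the two definitions coincide and one clarifying sentence is enough.
3. Exclude study-placed ART restorations from the filling limb, or report them separately.
4. Reconcile the outcome wording in Section 8.1.1 with the newly identified lesions of Section 7.2. This concerns how events are counted, not which lesions are treated.

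The cost is a few sentences and a derivation change if the codes are on file; Section 13.2.2 already has the data manager code the dental exams longitudinally after collection. The drawback is that codes 1-2 may be scored less reliably, so a shift from code 2 to code 3 between exams may partly reflect examiner variation. That is a reason to keep the stricter definition as the sensitivity analysis.
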